### **2.7.1.2 Disease-specific, daily efficacy assessment**

On a daily basis throughout the study, the patient uses an electronic diary / PEF meter to:

- Measure morning and evening PEF,
- Indicate the number of inhalations/day of salbutamol/albuterol or, levosalbutamol/levalbuterol for symptom relief,
- Record the number of inhalations/day of background product used,
- Record oral steroids use after bronchoscopy and for exacerbation event.

At screening (Visit 1), patients will be issued an electronic diary/PEF. Patients will be instructed on the use of the device, and written instructions on the use of the electronic PEF meter will be provided to the patients. In addition, the investigator will instruct the patients on how to record the following variables in the electronic PEF meter:

- AM PEF performed within 15 minutes after arising (between 5:30 AM and 12:00 PM) prior to taking any albuterol/salbutamol or levalbuterol/levosalbutamol,
- PM PEF performed in the evening (between 5:30 PM and 12:00 AM) prior to taking any albuterol/salbutamol or levalbuterol/levosalbutamol,
- Patients should try to withhold albuterol/salbutamol or levalbuterol/levosalbutamol for at least 6 hours prior to measuring their PEF,
- Three PEF efforts will be performed by the patient; all 3 values will be recorded by the electronic PEF meter, and the highest value will be used for evaluation.

Baseline AM PEF will be the mean AM measurement recorded for the 7 days prior to Visit 2, and baseline PM PEF will be the mean PM measurement recorded for the 7 days prior to Visit 2. There should be at least 4 days' measurement out of the 7 days for setting up the period stability limit/baseline, and the first dosing visit should be rescheduled until data for 4 days are available. In case less than 4 days' measurement is available during the 7 days prior to randomization, the baseline AM/PM PEF is the mean of the 4 AM/PM PEF prior to and closest to randomization during the whole screening period. For the daily measurements, calculation of periodical average specified in [Section 2.11.3](#) will be implemented.

Period stability limit is defined as the respective mean AM or PM PEF obtained over the last 7 days prior to Visit 2.

The exploratory endpoints for AM/PM PEF are the following ones:

- Absolute change from baseline in morning [AM]/evening [PM] peak expiratory flow [PEF] at Weeks 2, 4, 6, 8 and 12.

## 2.7.2 Analyses

The change from baseline in efficacy parameters will be analyzed using a MMRM approach based on the secondary PD population. All on-treatment data until Week 12/EOT will be taken into account, i.e., data measured before or on the last IMP date + 14 days. The model will include the fixed categorical effects of treatment group (dupilumab vs placebo), visit and treatment-by-visit interaction, the ICS dose level and the region, as well as the continuous fixed covariate of baseline efficacy endpoint and the baseline-by-visit interaction. This model will be run using SAS© Mixed procedure with an unstructured correlation matrix to model the within-patient errors. Parameters will be estimated using restricted maximum likelihood method with the Newton-Raphson algorithm. Denominator degrees of freedom will be estimated using Kenward-Roger adjustment. The between-group difference (dupilumab vs placebo) in LS-mean change from baseline at each visit the corresponding two-sided 90% CI, and p-values will be reported from this model.

If MMRM model fails to achieve convergence due to complexity of model specification, and given the low sample size, some fixed effects or interactions might be removed from the model; other covariance structures may be also tested.

No imputation will be performed for the MMRM model.

## 2.8 ANALYSIS OF SAFETY DATA

All safety analyses will be performed on the safety population, unless otherwise specified.

The safety analysis will be based on the reported adverse events and other safety information, such as clinical laboratory data, vital signs, ECG and physical examination.

All safety endpoints are considered as additional endpoints in this study.

### *Observation period*

The observation period will be divided into 4 epochs:

- The **screening** epoch is defined as the time from the signed informed consent date up to the time prior to the first administration of the IMP.
- The **treatment** epoch is defined as the time from the first administration of the IMP to the last administration of the IMP + 14 days or until rollover to the OLE study.
- The **residual treatment** epoch is defined as the time from the last administration of the IMP + 15 days to the last administration of the IMP + 98 days or until rollover to the OLE study.
- The **posttreatment** epoch is defined as the period of time starting the day after the end of the treatment-emergent adverse event period up to the end of the study (defined as last

protocol planned visit or the resolution/stabilization of all serious adverse events and adverse events of special interest).

The treatment-emergent adverse event (TEAE) period will include both treatment and residual treatment periods.

The on-study observation period is defined as the time from start of treatment until the end of the study (defined as last protocol planned visit or lost to follow-up or the resolution/stabilization of all serious adverse events and adverse events of special interest).

The summary of safety results will be presented by treatment group.

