### **1.1 STUDY DESIGN AND RANDOMIZATION**

PDY14192 is a Phase 2a, exploratory, multinational, multicenter, randomized, double-blind, placebo-controlled, parallel group study of repeated doses of dupilumab or placebo administered subcutaneously (SC) every 2 weeks (q2w) for 12 weeks in adult patients with persistent asthma who are receiving at minimum a medium to high dose of inhaled corticosteroid (ICS) in combination with long-acting beta-agonists (LABA). Patients requiring a third asthma controller are eligible. Both the patients and investigators will be blinded to assigned active drug or matching placebo.

After a screening phase of up to 6 weeks (5 weeks and optional addition of 7 days), patients will be centrally randomized (using allocation from block randomization schedule) via Interactive Voice Response System/Interactive Web Response System (IVRS/IWRS) in a 1:1 randomization ratio to dupilumab 300 mg q2w in 2 mL or placebo q2w in 2 mL. Randomization will be stratified by ICS dose level (medium, high) and region (North America, Europe).

During the study, patients will undergo 2 bronchoscopy procedures (one prior to the initiation of study drug and the other after 12 weeks of treatment) for the collection of bronchial biopsy, bronchial brushing and bronchoalveolar lavage fluid samples.

Approximately 42 patients will be randomized to dupilumab or placebo (around 21 patients per group) with at least 21 patients receiving treatment with high dose of ICS and no more than 8 patients with baseline blood eosinophils < 150 cells/ $\mu$ L (i.e., 0.15 Giga/L).

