## 1.4 STUDY PLAN

The clinical trial consists of three periods:

- **Screening Period** (5 weeks and potentially additional up to 7 days): to determine a patient's eligibility status or scheduling of bronchoscopy and establish the level of asthma control before randomization. During the screening period, a bronchoscopy procedure is performed to acquire baseline samples.
- **Randomized Treatment Period** (12 weeks and potentially additional up to 4 weeks in the case the bronchoscopy at week 12 has to be postponed to week 14 or 16): to treat with dupilumab or placebo SC injection.
- **Post-treatment Period** (12 weeks): to monitor patients' statuses when off study drug treatment for patients not participating in the open label extension (OLE) LTS12551 study. Eligible patients participating in the OLE study will enter the study after completion of the EOT visit assessments. The post-treatment analyses for patients who enter the OLE study will be described in a separate SAP.

Figure 1 - Graphical study design

\*R: Randomization 1:1  
BC: Bronchoscopy  
IMP: Investigational Medicinal Product administration  
EOT: End-Of-Treatment visit  
EOS: End-Of-Study visit  
Visit windows for visits after Day 1 are +/- 3 days  
\*\*If a patient is unable to undergo a bronchoscopy at Week 12, the EOT visit may be postponed and up to 2 additional doses of IMP may be administered.

Refer to the [Appendix A](#) for the detailed study flow chart.

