## 2.5 PRIOR/CONCOMITANT MEDICATION/THERAPY

All medications taken within 3 months before screening and until the end of the study, including asthma controller medications and systemic corticosteroids, are to be reported in the case report form (CRF) pages.

All medications will be coded using the World Health Organization-Drug Dictionary (WHO-DD) version currently in effect at Sanofi at the time of database lock.

- Prior medications are those the patient used prior to the first IMP injection. Prior medications can be discontinued before the first administration or can be ongoing during treatment phase.
- Concomitant medications are any treatments received by the patient concomitantly to the IMP, from the first administration of IMP to the last administration of IMP + 98 days or till rollover to the OLE study.
- Post-treatment medications are those the patient took in the period from the last administration of IMP + 99 days to the end of the study.

A given medication can be classified as a prior medication, concomitant medication and post-treatment medication at the same time.

The prior and concomitant medications will be presented for the randomized population.

Medications will be summarized by treatment group according to the WHO-DD dictionary, considering the first digit of the anatomic category (ATC) class (anatomic category) and the first 3 digits of the ATC class (therapeutic category). All ATC codes corresponding to a medication will be summarized, and patients will be counted once in each ATC category (anatomic or therapeutic) linked to the medication. Therefore patients may be counted several times for the same medication.

The table for prior medications will be sorted by decreasing frequency of ATC followed by all other therapeutic classes based on the overall incidence across treatment groups. In case of equal frequency regarding ATCs (anatomic or therapeutic categories), alphabetical order will be used.

Concomitant medication received during the first IMP to the last IMP + 14 days and concomitant medication received during the first IMP to the last IMP + 98 days will be summarized separately. The tables for concomitant medications will be sorted by decreasing frequency of ATC followed

by all other therapeutic classes based on the incidence in the dupilumab group. In case of equal frequency regarding ATCs (anatomic or therapeutic categories), alphabetical order will be used.

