### **2.8.1.2 General information**

The primary focus of adverse event reporting will be on TEAEs. Pretreatment adverse events will be described separately.

If an adverse event date/time of onset (occurrence, worsening, or becoming serious) is incomplete, an imputation algorithm will be used to classify the adverse event as pretreatment or treatment-emergent. The algorithm for imputing date/time of onset will be conservative and will classify an adverse event as treatment emergent unless there is definitive information to determine it is pretreatment. Details on classification of adverse events with missing or partial onset dates are provided in [Section 2.11.5](#).

Multiple occurrences of the same event in the same patient will be counted only once in the tables within a treatment phase. The denominator for computation of percentages is the safety population within each treatment group. Sorting will be based on results for the dupilumab group.

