### **2.8.2 Clinical laboratory evaluations**

#### **Parameters**

The clinical laboratory data consists of blood analysis, including hematology, clinical chemistry serology, and urinalysis. Clinical laboratory values will be analyzed after conversion into standard international units. International units will be used in all listings and tables.

Blood samples for clinical laboratories will be taken at both screening visits, Week 4, Week 8, Week 10 (selected parameters, see below), Week 12/EOT, and for patients who do not enter the OLE, at Week 16 and EOS.

The laboratory parameters will be classified as follows:

- Hematology
  - Red blood cells and platelets and coagulation: hemoglobin, hematocrit, platelet count, prothrombin time, partial thromboplastin time (PTT) at Visit 1 only.
  - White blood cells: total white blood cell count with five-part differential count (neutrophils, eosinophils, basophils, monocytes and lymphocytes), and total red blood cell count.
- Clinical chemistry
  - Metabolism: glucose, total cholesterol, total protein, creatine phosphokinase.
  - Electrolytes: sodium, potassium, chloride, bicarbonate.
  - Renal function: creatinine, blood urea nitrogen, uric acid.
  - Liver function: alanine aminotransferase (ALT), aspartate aminotransferase (AST), alkaline phosphatase, lactate dehydrogenase, total bilirubin (in case of values above the normal range, differentiation in conjugated and non-conjugated bilirubin), albumin.
  - Anti-nuclear antibody (ANA) at Visit 1 for all patients and at Week 10 only for patients who plans to enter the OLE.
  - Anti-ds DNA antibody will be tested if ANA is positive ( $\geq 1:160$  titer).
  - Pregnancy test: serum  $\beta$ -human chorionic gonadotropin will be performed at screening (Visit 1) in women of childbearing potential.

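### Crude TEAE and laboratory and vital-sign PCSA percentages pool windows of about 12 weeks (patients who roll over) and about 24 weeks (completers who do not), with no treatment-epoch table or person-time rate beside them

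*SAP*

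**What the plan says.** - **Window.** SAP section 2.8 (Observation period) defines a treatment epoch, up to last dose + 14 days or rollover, and a residual treatment epoch: "last administration of the IMP + 15 days to the last administration of the IMP + 98 days or until rollover to the OLE study". The two are then joined: "The treatment-emergent adverse event (TEAE) period will include both treatment and residual treatment periods".
- **Rollover.** Section 1.4: "Eligible patients participating in the OLE study will enter the study after completion of the EOT visit assessments". The 12-week post-treatment period is only for patients who do not enter the OLE.
- **TEAE percentages.** Section 2.8.1.2: "The denominator for computation of percentages is the safety population within each treatment group". Sections 2.8.1.3 and 2.8.1.5 report number (%) of patients.
- **PCSA percentages.** Section 2.8 (rules for PCSAs) and sections 2.8.2 and 2.8.3 count a patient with a PCSA at any time in the TEAE period, over the patients assessed for that parameter in that period.
- **Laboratory schedule.** Section 2.8.2 gives the last sampling times as "Week 12/EOT, and for patients who do not enter the OLE, at Week 16 and EOS".
- **Where a split exists.** Section 2.5 does separate the two windows, but only for medication: "Concomitant medication received during the first IMP to the last IMP + 14 days and concomitant medication received during the first IMP to the last" dose + 98 days are summarized separately.

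**The concern.** Two patients with the same risk contribute different lengths of observation to the same percentage, depending on whether they enter the OLE. Rollover is a post-randomization event that can depend on response or tolerability, so its share may differ between arms. An arm with fewer rollovers would then be observed for longer on average. It would also have more Week 16 and end-of-study draws at which to cross a PCSA limit or a peak eosinophil threshold, and so could show more events with no true difference. Safety and tolerability compared with placebo is the additional objective in section 1.2.2, and these percentages are its planned summary. Even without an imbalance, the result is neither a 12-week nor a 24-week incidence, which makes it hard to set beside other studies.

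**Working it through.** **1. Window lengths.** Section 1.1 gives dosing as "administered subcutaneously (SC) every 2 weeks (q2w) for 12 weeks". The last regular dose is therefore at Week 10, 70 days after the first (inferred from the interval and the duration).

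- Rollover after EOT: 70 + 14 = 84 days = 12 weeks.
- Completer without rollover: 70 + 98 = 168 days = 24 weeks. This agrees with the Week 24 end-of-study visit in section 2.7.1.1.
- Ratio: 168/84 = 2.0.
- Postponed EOT (section 1.4: "the EOT visit may be postponed and up to 2 additional doses of IMP may be administered"): with one extra dose, 14 versus 26 weeks (ratio 1.86); with two, 16 versus 28 weeks (ratio 1.75).
- Early stopper after *k* doses: 14(*k* - 1) + 98 days, which is 14 weeks for *k* = 1 and 22 weeks for *k* = 5.

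**2. Effect on a crude TEAE percentage.** Assumptions, none of them from the SAP: 21 treated patients per arm, all completing; the same constant hazard in both arms, on and off drug; rollover unrelated to risk. Let p12 be the 12-week risk and r the rollover share.

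- p24 = 1 - (1 - p12)²
- Crude percentage = r × p12 + (1 - r) × p24
- Spurious difference = (difference in r) × (p24 - p12)

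| p12 | p24 | 19/21 vs 15/21 (difference 4/21) | 19/21 vs 13/21 (difference 6/21) |
|---|---|---|---|
| 40% | 64% | 4.6 points | 6.9 points |
| 50% | 75% | 4.8 points | 7.1 points |
| 60% | 84% | 4.6 points | 6.9 points |

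At p12 = 50%, for example, the crude figures are 52.4% and 57.1%. Mean scheduled observation is (19 × 12 + 2 × 24)/21 = 13.1 weeks against (15 × 12 + 6 × 24)/21 = 15.4 weeks.

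**3. Lower risks and other rollover shares.**

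| p12 | 90% vs 80% | 90% vs 70% | 90% vs 50% |
|---|---|---|---|
| 30% | 2.1 points | 4.2 points | 8.4 points |
| 10% | 0.9 points | 1.8 points | 3.6 points |

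Equal rollover gives a difference of zero, but the level still moves. At p12 = 30% it is 32.1% with 90% rollover and 40.5% with 50%.

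**4. Laboratory PCSAs.** Full draws after baseline are at Weeks 4, 8 and 12/EOT, with Week 16 and end of study added for patients who do not roll over. Assume a 10% chance per draw and independent draws. Three draws give 1 - 0.9³ = 27.1% and five give 1 - 0.9⁵ = 41.0%. With 19/21 versus 15/21 the spurious difference is 13.9 × 4/21 = 2.6 points. Abnormalities that persist within a patient would make it smaller.

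**5. Search for an offsetting table.** The only display by exposure in the safety sections is optional and covers liver PCSAs (section 2.8.2, Drug-induced liver injury). Exposure in section 2.4.1 is last dose - first dose + 14 days, so it does not count off-drug follow-up.

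**The case against.** A reader might infer that the safety comparison is biased as planned, or that every safety output is affected. The SAP supports neither.

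- **Bias is conditional.** It needs rollover that differs by arm or relates to risk differently by arm. The SAP gives no rate, and the splits above are assumptions.
- **Scope is limited.** No ECG is scheduled after Week 12/EOT, so ECG PCSAs hardly change. By-visit summaries do not use the window. Some counts in section 2.8.1.5 are not defined by it, such as serious events counted whether or not treatment-emergent, and injection site reactions by injection.
- **Size is modest.** One patient in 21 is 4.8 points. At 50% incidence the standard error of the difference is √(2 × 0.5 × 0.5/21) = 15.4 points, so a 5-point shift is about one third of it.
- **The analysis is descriptive.** It belongs to an exploratory Phase 2a study and no test or decision rule uses these percentages. Rollover counts by arm and event listings are planned.
- **The window is deliberate.** Table 1 aligns the TEAE period with another study, and ending observation when open-label treatment starts is not an error.
- **The treatment epoch is not a common window.** After one dose it lasts about 14 days and for a completer about 84, so it depends on discontinuation.

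All of this stands. It limits the claim and argues against replacing the main tables. It does not supply a summary that accounts for unequal observation: rollover counts alone do not let a reader correct the percentages.

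**Conclusion.** The concern holds as a gap in presentation. Crude TEAE percentages, laboratory and vital-sign PCSA percentages, and the peak blood eosinophil thresholds mix observation windows that differ about two-fold between patients who roll over and completers who do not. Nothing planned beside them adjusts for time at risk or limits the window to the treatment epoch.

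The size is conditional. It is about 5 percentage points, or about one patient per arm, if the arms have equal constant hazards, a 12-week incidence of 40-60%, and rollover of 19/21 versus 15/21. With equal rollover unrelated to risk, the comparison with placebo is undistorted and only the level is affected. The window lengths follow from the SAP. The rollover shares, incidences and constant hazard do not. The change is worth making because the epochs are already defined and section 2.5 already makes the same split for medication.

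**What to change.** Keep the present TEAE-period definition, tables and listings. In sections 2.8.1.3 and 2.8.1.5 and in the laboratory and vital-sign PCSA sections, add:

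1. The overview, SOC/PT, AESI and PCSA tables limited to the treatment epoch (first dose to last dose + 14 days, or rollover if earlier). Show residual-epoch events separately, with the patients followed in that epoch as denominator.
2. For the pooled TEAE period, patient-years at risk by arm, counting the off-drug follow-up, and the number of patients with event per 100 patient-years.

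The cost is SAP wording and a few more outputs from data already collected. The drawbacks should be stated with the tables: residual-epoch denominators may be small and self-selected, the treatment epoch is still shorter for early stoppers, and the rates assume a roughly constant hazard across time on and off drug.

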### ***General common rules***

- The baseline value is defined as the last available value before the first dose of IMP.
- The analysis of the safety variables will be essentially descriptive and no systematic testing is planned.
- All safety values will be assigned to the theoretical visit; unscheduled visit measurements will be included in the computation of baseline if occurred before the 1st IMP and will be taken into account in the PCSAs analyses, but will not be included in any by-visit summaries or statistical models (only scheduled values will be taken into account).

### ***General common rules related to PCSA for clinical laboratory evaluations, vital signs, and ECG***

- The potentially clinically significant abnormality (PCSA) values are defined as abnormal values considered medically important by the Sponsor according to predefined criteria/thresholds based on literature review and defined by the Sponsor for clinical laboratory tests, vital signs, and ECG ([Appendix F](#)).
- PCSA criteria will determine which patients has at least 1 PCSA during the treatment-emergent adverse event period, taking into account all evaluations performed during the treatment-emergent adverse event period, including nonscheduled or repeated evaluations. The number of all such patients will be the numerator for the on-treatment PCSA percentage.
- The treatment-emergent PCSA denominator by group for a given parameter will be based on the number of patients assessed for that given parameter in the treatment-emergent adverse event period by treatment group on the safety population. Number (%) of patients with at least 1 PCSA will be summarized regardless of baseline PCSA status and also by baseline PCSA status.
- For quantitative safety parameters based on central laboratory/reading measurements, descriptive statistics will be used to summarize results and change from baseline values by visit and treatment group.

